7.3.5.1. Statistical Methodology Specification

Other Secondary Statistical Analyses for change from baseline until week12 after first treatment	
Endpoint(s)	
	
 • Change from baseline • Daily average number of urinary incontinence • Average volume voided per micturition • Daily average number of urinary urgency incontinence episodes • Daily average number of voids • Daily average number of urgency episodes • Daily average number of nocturia episodes • Daily average number of severe urgency episodes • Daily average number of severe or moderate urgency episodes
Model Specification	
	
 • The endpoints will be analyzed using a mixed model for repeated measures (MMRM). • Terms fitted in the MMRM model will include:

Other Secondary Statistical Analyses for change from baseline until week12 after first treatment

- Fixed, categorical effects: treatment, site, visit, baseline UUI episodes over 3 day diary (<= 9 or >= 10)*, treatment-by-visit interaction
- Fixed, continuous effects: baseline value, baseline-by-visit interaction

*; Baseline UUI episodes over 3-day diary (<= 9 or >= 10) is a stratification factor. This will be excluded for daily average number of urinary incontinence episodes and daily average number of urinary urgency incontinence episodes, because the strong correlation is expected between baseline values and a stratification factor.

- An unstructured variance structure will be used to model the within-subject errors, shared across treatments.
- The Kenward-Roger option in SAS PROC MIXED will be used to estimate denominator degrees of freedom and standard errors.

Model Checking & Diagnostics

- Refer to [7.1.5](#)

Model Results Presentation

- Adjusted means (least square means) and corresponding standard errors of means will be presented for each treatment by visit, together with estimated treatment differences (GSK1358820 – Placebo), the corresponding 95% confidence intervals and p-values.

Data included in Model

- The dataset including only data until week 12 after the first treatment will be used.

Other Secondary Statistical Analyses for change from baseline and after week12 after first treatment

Endpoint(s)

- Change from baseline
- Daily average number of urinary incontinence
- Average volume voided per micturition
- Daily average number of urinary urgency incontinence episodes
- Daily average number of voids
- Daily average number of urgency episodes
- Daily average number of nocturia episodes
- Daily average number of severe urgency episodes
- Daily average number of severe or moderate urgency episodes

Model Specification

- The endpoints will be analyzed using an analysis of covariance (ANCOVA) model.
- Terms fitted in the ANCOVA model will include:
 - Fixed, categorical effects: treatment, site, baseline UUI episodes over 3 day diary (<= 9 or >= 10)*
 - Fixed, continuous effects: baseline value

*; Baseline UUI episodes over 3-day diary (<= 9 or >= 10) is a stratification factor. This will be excluded for daily average number of urinary incontinence episodes and daily average number of urinary urgency incontinence episodes, because the strong correlation is expected between

Other Secondary Statistical Analyses for change from baseline and after week12 after first treatment
baseline values and a stratification factor.

 The Kenward-Roger option in SAS PROC MIXED will be used to estimate denominator degrees of freedom and standard errors.
Model Results Presentation

 Adjusted means (least square means) and corresponding standard errors of means will be presented for each treatment by visit, together with estimated treatment differences (GSK1358820 – Placebo), the corresponding 95% confidence intervals and p-values.

Other Secondary Statistical Analyses for change from baseline after first treatment
Endpoint(s)

 Change from baseline KHQ domain score (role limitations, social limitations) OABSS total score
Model Specification

 Same as "Other Secondary Statistical Analyses for change from baseline and percent change from baseline after week12 after first treatment".
Model Results Presentation

 Same as "Other Secondary Statistical Analyses for change from baseline and percent change from baseline after week12 after first treatment".

Other Secondary Statistical Analyses for Binary data
Endpoint(s)

 Proportion of subjects attaining 100%, $\geq 75\%$ and $\geq 50\%$ reduction from baseline in the daily average of urinary incontinence episodes Proportion of subjects attaining 100%, $\geq 75\%$ and $\geq 50\%$ reduction from baseline in the daily average of urinary urgency incontinence episodes
Model Specification

 The above endpoints will be analyzed using the Cochran-Mantel-Haenszel test (CMH test) stratified by a stratification factor at each visit
Model Results Presentation

 The number and percent of subjects who met each endpoint will be summarized by treatment and visit. The Mantel-Haenszel estimate of common odds ratio and its 95% confidence intervals will be estimated. The p-values by CMH test will be presented at each visit. Plots of proportion of subjects attaining 100% reduction will be generated for each treatment until week 12 after 1st treatment. As same for proportion of subjects attaining $\geq 75\%$ and $\geq 50\%$ reduction will be generated.
Handling Missing Data of Change from Baseline in the urinary diary

 If a subject has missing data due to any reasons (e.g., early withdrawal), then this subject will be regarded as NOT attaining 100%, $\geq 75\%$ and $\geq 50\%$ reduction from baseline in the daily

Other Secondary Statistical Analyses for Binary data

average of urinary (urgency) incontinence episodes (i.e., regarded as a non-responder). This rule will be applied to the data until week 12 after 1st treatment. Missing data after 12 week after 1st treatment will not be imputed and treated as missing.

- This rule will be called as “DO=NR” rule. DO=NR means dropout equals to non-responder.

Other Secondary Statistical Analyses for Binary data for TBS**Endpoint(s)**

- Proportion of subjects with positive response on the TBS

Model Specification

- The above endpoints will be analyzed using the Cochran-Mantel-Haenszel test (CMH test) stratified by a stratification factor at each visit

Model Results Presentation

- The number and percent of subjects who met each endpoint will be summarized by treatment and visit.
- The Mantel-Haenszel estimate of common odds ratio and its 95% confidence intervals will be estimated.
- The p-values by CMH test will be presented at each visit.

Handling Missing Data of TBS

- Missing data due to any reasons (e.g., early withdrawal) will be regarded as no positive response. This rule will be applied to the data until week 12 after 1st treatment. Missing data after 12 week after 1st treatment will not be imputed and treated as missing.
- This rule will be called as “DO=NR” rule. DO=NR means dropout equals to non-responder.

Other Secondary Statistical Analyses for Categorical data**Endpoint(s)**

- Change from baseline of maximum urgency intensity
- Proportions of patients with maximum urgency intensity

Model Specification

- The above endpoints will be analyzed using van Elteren test stratified by a stratification factor at each visit

Model Results Presentation

- Change from baseline of maximum urgency intensity: The number and percent of subjects who met following category will be summarized by treatment and visit.
 - 3 point improvement
 - 2 point improvement
 - 1 point improvement
 - No Change
 - 1 point worsening
 - 2 point worsening
 - 3 point worsening
- For calculation of above category, the following values will be used for each intensity
 - 0: None
 - 1: Mild

Other Secondary Statistical Analyses for Categorical data

 ○ 2: Moderate ○ 3: Severe 
 ● Proportions of patients with maximum urgency intensity: The number and percent of subjects will be summarized by maximum urgency intensity category (None, Mild, Moderate or Severe) in the visit. No statistical test will be done for this endpoint. ● The p-values by van Elteren test will be presented at each visit for change from baseline of maximum urgency intensity.
Baseline Observation Carried Forward for Missing Data

 ● Missing data until week 12 after the first treatment will be imputed by baseline observation carried forward (BOCF). This rule will be applied to the data until week 12 after 1st treatment. Missing data after 12 week after 1st treatment will not be imputed and treated as missing.

Other Secondary Statistical Analyses for Time to Event data
Endpoint(s)

 ● Time to the subject's first request for 2nd treatment from the day of 1st treatment ● Time to the subject's first qualification for 2nd treatment from the day of 1st treatment
Model Specification

 ● The above endpoints will be analyzed using the log-rank test stratified by a stratification factor. ● The above endpoints will be displayed as Kaplan-Meier curves. ● In order to estimate the hazard ratio to placebo and its 95% confidence interval, Cox proportional hazard model will be used. This Cox model include treatment and a stratification factor as fixed effect.
Model Results Presentation

 ● The p-values by log-rank test will be presented. ● The hazard ratio to placebo and its 95% confidence interval will be estimated.
Definition of Event in these endpoints

Time to the subject's first request for 2nd treatment from the day of 1st treatment
 
 ● Event is considered to occur at "Date of subject status" in eCRF when the following items meet for the first time. 
 ○ Answer to question "Did patient initiate request for retreatment?" in eCRF = "Yes" ○ Regardless of answer to question "Did patient qualify for retreatment?" in eCRF 
Time to the subject's first qualification for 2nd treatment from the day of 1st treatment
 
 ● Event is considered to occur at "Date of subject status" in eCRF when the following items meet for the first time. 
 ○ Answer to question "Did patient initiate request for retreatment?" in eCRF = "Yes" ○ Answer to question "Did patient qualify for retreatment?" in eCRF = "Yes" 
(Time to the subject's first request for 2nd treatment from the day of 1st treatment) = (the earliest date when "Yes" response to the eCRF question "Did patient initiate request for retreatment?" – the day of first treatment + 1

CONFIDENTIAL

204947

Other Secondary Statistical Analyses for Time to Event data
(Time to the subject's first qualification for 2nd treatment from the day of 1st treatment) = (the earliest date when "Yes" response to the eCRF question "Did patient qualify for retreatment?") – the day of first treatment + 1
Censoring

• If the subject withdraws the study prematurely before receiving 2nd treatment, this subject will be regarded as censored at the date of study withdraw.• If the subject completes the study without request for the 2nd treatment, the subject will be regarded as censored at the date of study complete.

8. SAFETY ANALYSES

The safety analyses will be based on the “Safety” population, unless otherwise specified. In detail, each Safety population will be used for each study phase as below table. In principle, summaries for TC1 will be only by treatment group, and summaries for GTC1, GTC2, GTC3 and Overall will be by treatment group and its total.

For AEs:

Study phase	Population	Summary Group
TC1	SPDB	By treatment group
GTC1	SP1	By treatment group and total
GTC2	SP2	By treatment group and total
GTC3	SP3	By treatment group and total
Overall	SP1	By treatment group and total

NOTES:

- The definition of population is described in [Analysis Populations](#).

For other than AEs:

Study phase	Population	Summary Group
TC1	SPDB	By treatment group
GTC1, GTC2, GTC3	SP1	By treatment group and total

NOTES:

- The definition of population is described in [Analysis Populations](#).

Safety data from unscheduled visit will not be included in safety analysis (but included in listing), and safety data at last visit will be treated as Study Exit in safety analyses (but treated as Withdrawal in listing).

Visit displayed in safety analyses will be summarized below table for study phases and endpoints. SPDB (for TC1) and SP1 (for GTC1, GTC2 and GTC3) will be used for these summaries. Separate displays will be provided for TC1 and for GTCs (GTC1, GTC2 and GTC3).

Endpoints	Study phase	Study visit displayed in safety analyses table
Vital Sign	TC1	Baseline, Week 2, Week 6, Week 12, Week 18, Week 24, Week 30, Week 36, Week42, Study exit
	GTC1	Study baseline, Qualification for GTC1 [1], Week 0 [1], Week 2, Week 6, Week 12, Week 18, Week 24, Week 30, Week 36, Week42, Study exit
	GTC2	Qualification for GTC2, Week 0, Week 2, Week 6, Week 12, Week 18, Week 24, Week 30, Study exit
	GTC3	Qualification for GTC3, Week 0, Week 2, Week 6, Week 12, Week 18, Study exit
Clinical laboratory (chemistry and hematology), ECG	TC1	Baseline, Week 12, Study exit
	GTC1	Study baseline, Qualification for GTC1 [1], Week 12, Study exit

CONFIDENTIAL

204947

Endpoints	Study phase	Study visit displayed in safety analyses table
	GTC2	Qualification for GTC2, Week 12, Study exit
	GTC3	Qualification for GTC3, Week 12, Study exit
Body Weight	TC1	Baseline, Study exit
	GTC1	Study baseline, Qualification for GTC1 [1], Study exit
	GTC2	Qualification for GTC2, Study exit
	GTC3	Qualification for GTC3, Study exit
PVR	TC1	Baseline, Week 2, Week 6, Week 12, Week 18, Week 24, Week 30, Week 36, Week42, Study exit
	GTC1	Study baseline, Qualification for GTC1 [1], Week 2, Week 6, Week 12, Week 18, Week 24, Week 30, Week 36, Week42, Study exit
	GTC2	Qualification for GTC2, Week 2, Week 6, Week 12, Week 18, Week 24, Week 30, Study exit
	GTC3	Qualification for GTC3, Week 2, Week 6, Week 12, Week 18, Study exit

NOTES:

- Baseline means study baseline defined as [5.2](#).
- Study baseline will be used for the derivation of change from baseline
- Urinalysis results will be displayed by using worst case results post-baseline relative to baseline for protein and occult blood urinalysis only in accordance with IDSL standards rationale, not by visit
- Study exit includes withdrawal.
- [1]: only for subjects with Placebo at TC 1

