#### **7.4.7. Post-void residual (PVR) urine volume**

PVR urine volume will be assessed by ultrasound or bladder scan after subjects perform a voluntary void according to the study schedule. PVR urine volume can be assessed at any other time depending on clinical need. PVR measurements will not be done by catheterization.

Should a PVR urine volume indicate a clinically meaningful elevation, subjects should be asked to void once again (allowing the subjects sufficient time to void) and the PVR urine volume will then be reassessed. For subjects who have a PVR urine volume measurement repeated, only the repeat value should be recorded in the case report form (CRF).

If increased PVR is noted at a scheduled visit or at an unscheduled visit, proper procedures should be conducted according to the Guidance about the Management of PVR Urine Volume (Appendix 5).

The details of the Guidance about the Management of PVR Urine Volume are described below. Post-treatment PVR is divided into 3 categories:

- $< 200$  mL
- $\geq 200$  mL and  $< 350$  mL
- $\geq 350$  mL

The need for an additional assessment visit is assessed based on the PVR category mentioned above. The need for clean intermittent catheterization (CIC) is also dependent on the PVR as well as subject's symptoms. The objective of the guidance is to ensure that subjects are appropriately followed up and CIC is only initiated when required (while also ensuring that any unnecessary intervention is limited). However, the guidance does not preclude further actions if the investigators/subinvestigators deem the actions to be necessary.

The details are as follows:

1. PVR  $< 200$  mL

No protocol required action needs to be taken. Subjects will continue to be assessed as per the schedule of visits and procedures.

2. PVR  $\geq 200$  mL and  $< 350$  mL

If a PVR of  $\geq 200$  mL but  $< 350$  mL is identified at any post-treatment visit, the investigators/subinvestigators will assess the subject for any spontaneously reported associated symptoms (such as voiding difficulties or sensation of bladder fullness), with the resulting action to be as follows:

- a. If a subject reports associated symptoms that in the opinion of the investigators/subinvestigators require CIC to be initiated, then CIC should be initiated and managed according to the Guidance about the Management of PVR Urine Volume.

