- b. If a subject does not report any associated symptoms or if they report associated symptoms that, in the opinion of the investigators/subinvestigators, do not require CIC, the subject will be seen at an additional visit 1 week later, when the PVR and any associated symptoms will be reassessed. In addition, a urine analysis with a urine reagent strip as well as urinalysis, urine culture and sensitivity test at the central laboratory will be performed. Based on the test results at this visit, the following procedures will be conducted:
  - 1) If the PVR is increasing and is associated with symptoms, that in the opinion of the investigators/subinvestigators require CIC, then CIC should be initiated and managed according to the Guidance about the Management of PVR Urine Volume.
  - 2) If the PVR is  $\geq 350$  mL then CIC should be initiated and managed according to the Guidance about the Management of PVR Urine Volume.

- 3) If the PVR is increasing but is not associated with symptoms or is associated with symptoms that in the opinion of the investigators/subinvestigators do not require CIC, then the subject will be seen 1 week later to determine if CIC has become warranted based on PVR and/or any associated symptoms. The following procedures will be conducted at this additional visit:
  - A urine reagent strip, and urinalysis, urine culture and sensitivity test at the central laboratory will be collected.
  - If the investigators/subinvestigators judge that CIC should be initiated, then CIC should be initiated and managed according to the Guidance about the Management of PVR Urine Volume.
  - If CIC is not initiated and PVR continues to increase, the investigators/subinvestigators will determine whether the subject will be followed at regularly scheduled study visits or whether additional visits should occur.
- 4) If the PVR is decreasing or is unchanged then the subject will continue to be assessed per the schedule of visits and procedures

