### 3. $PVR \geq 350 \text{ mL}$

If a PVR of  $\geq 350 \text{ mL}$  is identified at any post-treatment visit (regardless of symptoms) then CIC will be initiated according to the Guidance about the Management of PVR Urine Volume.

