#### Initiation of CIC

CIC should only be initiated when one of the following criteria is fulfilled:

- PVR is  $\geq 350 \text{ mL}$  at any post treatment visit, regardless of reports of associated symptoms by subjects; or
- PVR is  $\geq 200 \text{ mL}$  and  $< 350 \text{ mL}$  and the subject spontaneously reports associated symptoms (e.g., voiding difficulties and sensation of bladder fullness) that in the opinion of the investigators/subinvestigators require CIC.

The following will occur when initiating CIC:

- 1) CIC should be performed using sterile, single-use catheters.
- 2) An adverse event of urinary retention should be recorded.
- 3) A urine analysis with a urine reagent strip as well as urinalysis, urine culture and sensitivity test at the central laboratory should be performed. In addition, these tests and analyses will be performed at scheduled visits after CIC is initiated.
- 4) The subject should be seen at a follow-up visit 1 week later, when the results of PVR measurement, associated symptoms, and a urine analysis with a urine reagent strip are

reassessed while urinalysis, urine culture and sensitivity test are performed for reassessment at the central laboratory. The investigators/subinvestigators will determine whether the subject should then be followed at regularly scheduled study visits or whether additional visits should occur.

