Table below shows the assessment window which applied to safety data at week 48 visit and withdrawal visit. Safety data at week 48 visit or withdrawal visit will be used as data of the visit within an assessment window, only if safety data for the planned scheduled visit is missing.

This assessment window will not be applied to any safety data at other visits. This means safety data except for week 48 visit and withdrawal visit will be only used as visit collected in eCRF.

Note that as described in section 8, safety data at last visit (typically, this is week 48 visit or withdrawal visit) will be also treated as study exit.

Rationale: For example, if a given subject receive 2nd treatment at week 36 after 1st treatment and complete study (i.e., complete week 48 visit), data for week 48 visit will be entered in “Week 48” page in eCRF, not in “Week 12 from 2nd treatment” page. In this case, data for week 12 from 2nd treatment seems to be missing in eCRF, but this is not true. This is the case for other situations. In order to summarize safety data at week 48 visit or withdrawal visit appropriately in a given TC or GTCs, this assessment window is needed.

Analysis Set / Domain	Parameter (if applicable)	Target Number of Days from Day 1 in each TC/GTC	Analysis Window		Analysis Timepoint in appropriate study phase (TC1 or GTCs)
			Beginning Timepoint	Ending Timepoint	
e.g. “Safety”, “Efficacy” or list specific domains if required	e.g. “All” or list specific parameters (i.e. tests) if required	The target or most desired relative day or relative time value for a given visit. e.g. “Day 7”	e.g. “Day 1”	e.g. “Day 10”	e.g. VISIT 1
Safety		Day 15	Day 12	Day 18	Week 2
Safety		Day 43	Day 36	Day 50	Week 6
Safety		Day 85	Day 78	Day 92	Week 12
Safety		Day 127	Day 120	Day 134	Week 18
Safety		Day 169	Day 162	Day 176	Week 24
Safety		Day 211	Day 204	Day 218	Week 30

CONFIDENTIAL

204947

Analysis Set / Domain	Parameter (if applicable)	Target Number of Days from Day 1 in each TC/GTC	Analysis Window		Analysis Timepoint in appropriate study phase (TC1 or GTCs)
			Beginning Timepoint	Ending Timepoint	
Safety		Day 253	Day 246	Day 260	Week 36
Safety		Day 295	Day 288	Day 302	Week 42
Safety		Day 337	Day 330	Day 343	Week 48

NOTES :

- Day 1 is the treatment date in each TC/GTC

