11.5.2. Reporting Standards

General	

 The current GSK Integrated Data Standards Library (IDSL) will be applied for reporting, unless otherwise stated (IDSL Standards Location: https://spope.gsk.com/sites/IDSLLibrary/SitePages/Home.aspx): 
 4.03 to 4.23: General Principles 5.01 to 5.08: Principles Related to Data Listings 6.01 to 6.11: Principles Related to Summary Tables 7.01 to 7.13: Principles Related to Graphics Do not include subject level listings in the main body of the GSK Clinical Study Report. All subject level listings should be located in the modular appendices as ICH or non-ICH listings 	
Formats	

 GSK IDSL Statistical Principles (5.03 & 6.06.3) for decimal places (DP's) will be adopted for reporting of data based on the raw data collected, unless otherwise stated. Numeric data will be reported at the precision collected on the eCRF. The reported precision from non eCRF sources will follow the IDSL statistical principles but may be adjusted to a clinically interpretable number of DP's. 	
Planned and Actual Time	

 Reporting for tables, figures and formal statistical analyses: 
 Planned time relative to dosing will be used in figures, summaries, statistical analyses and calculation of any derived parameters, unless otherwise stated. The impact of any major deviation from the planned assessment times and/or scheduled visit days on the analyses and interpretation of the results will be assessed as appropriate. Reporting for Data Listings: 
 Planned and actual time relative to study drug dosing will be shown in listings (Refer to IDSL Statistical Principle 5.05.1). Unscheduled or unplanned readings will be presented within the subject's listings. 	
Unscheduled Visits	

 Unscheduled visits will not be included in summary tables and/or figures. All unscheduled visits will be included in listings. 	

CONFIDENTIAL

204947

Descriptive Summary Statistics	
Continuous Data	Refer to IDSL Statistical Principle 6.06.1 N, mean, standard deviation (or standard error), median, minimum and maximum.
Categorical Data	N, n, frequency, %
Graphical Displays	
• Refer to IDSL Statistical Principals 7.01 to 7.13.	

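### Read literally, the SAP drops off-schedule PVR values from the maximum PVR in treatment cycle 1, so a subject whose peak fell between planned visits is placed in too low a category in Tables 3.134 and 3.139 (minor)

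*SAP*

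**What the plan says.** The relevant rules read the same in the April 2018 and July 2018 SAPs.

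- **Exclusion.** SAP section 8: "Safety data from unscheduled visit will not be included in safety analysis (but included in listing". SAP 11.5.2: "Unscheduled visits will not be included in summary tables and/or figures".
- **No re-slotting.** SAP 11.3.2 moves only week 48 and withdrawal data into visit windows; otherwise "safety data except for week 48 visit and withdrawal visit will be only used as visit collected in eCRF". The section 8 visit list for PVR in TC1 has baseline, the planned visits from week 2 to week 42, and study exit.
- **Tables concerned.** SAP 8.5.2 and 8.5.3 classify CIC users and subjects with urinary tract infection (UTI) by the category of their maximum PVR in TC1 (Tables 3.134 and 3.139). The categories are <100, 100 to <200, 200 to <350 and ≥350 mL. SAP 8.5.1 summarises PVR at CIC start (Table 3.129), with a value from 2 weeks before CIC as the fallback when none is available at the start.
- **Off-schedule PVR in the protocol.** After a value of 200 to <350 mL without CIC, protocol 7.4.7 says "the subject will be seen at an additional visit 1 week later, when the PVR and any associated symptoms will be reassessed". If PVR is still rising after a further week without CIC, the investigator decides "whether the subject will be followed at regularly scheduled study visits or whether additional visits should occur". The section also provides: "If increased PVR is noted at a scheduled visit or at an unscheduled visit, proper procedures should be conducted". If a PVR of 350 mL or more "is identified at any post-treatment visit (regardless of symptoms) then CIC will be initiated"; the CIC initiation criteria repeat that this applies "at any post treatment visit, regardless of reports of associated symptoms by subjects".
- **Explicit exceptions elsewhere.** SAP 5.2 admits unscheduled values for baseline, and SAP 8.3 admits them for worst-case urinalysis.

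**The concern.** A maximum is only as good as the set of values it is taken over. The protocol creates extra PVR measurements mainly in subjects whose PVR is already raised, and a peak can fall at one of them. The general exclusion removes those values from the quantity meant to describe how high PVR went. Worst-case urinalysis is the direct analogue, and there the SAP says in so many words that unscheduled values count. For maximum PVR it is silent.

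At stake is how Tables 3.134 and 3.139 relate CIC and UTI to PVR level, and which value enters Table 3.129. Protocol 9.4.2 promises CIC use by PVR category without saying which visits count, so the SAP has to say it.

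**Working it through.** The plan states no figure for this point, so there is none to reproduce. The check traces the rule and applies it to invented PVR profiles.

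**1. Where off-schedule PVR arises (protocol 7.4.7).** There are five occasions: 1 week after a value of 200 to <350 mL without CIC; a further week later if rising; 1 week after CIC start; 1 week after CIC stop; and any time on clinical need. None is in the Time and Events tables or the SAP visit list for PVR.

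**2. Effect on one subject.** Dropping values can only lower a maximum or leave it unchanged. Illustrative profiles (values in mL, assumed):

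| Profile | Planned-visit maximum | Maximum of all TC1 values |
|---|---|---|
| A: week 2 250; additional visit 380, CIC starts; week 6 150; week 12 60 | 250 → 200 to <350 | 380 → ≥350 |
| B: unscheduled day 8 400, CIC starts; week 2 180; week 6 90; week 12 60 | 180 → 100 to <200 | 400 → ≥350 |
| C: week 2 380; additional visit 300; week 6 120 | 380 → ≥350 | 380 → ≥350 |
| D: UTI; week 2 120; week 6 150; unscheduled day 60 260; week 12 90 | 150 → 100 to <200 | 260 → 200 to <350 |

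In profile A the triggering 200 to <350 mL value was at a planned visit. The planned-visit maximum is then at least 200 mL, and the only possible misplacement is across 350 mL. Falling below 200 mL (profile B) requires the raised value itself to be off schedule. Profile C is unaffected.

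**3. Table 3.129.** In profile A the 380 mL value at CIC start is excluded. The fallback then takes the week 2 value, 250 mL, from 1 week earlier. In profile B no planned post-treatment PVR precedes day 8, so the fallback has no post-treatment value to use.

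**4. Effect on row percentages.** Subjects without CIC or UTI lose off-schedule peaks too, and the SAP does not state the denominator. Suppose the row denominators are all subjects in the row, with UTI in 4/10 (40%) at ≥350 mL and 6/20 (30%) at 200 to <350 mL (invented counts).

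- Two subjects without UTI drop a row: 4/8 = 50% and 6/22 = 27%. UTI looks more tied to high PVR.
- Two subjects with UTI drop a row: 2/8 = 25% and 8/22 = 36%. UTI looks less tied to high PVR.

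**5. Scale of the tables, not of the error.** Protocol 4.6.1 gives pooled retention rates of 7.1% v 0.5% and UTI rates of 26.4% v 10.1%. Per 120 subjects:

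- Retention: 120 × 0.071 = 8.5 active (95% binomial range 3 to 14); 120 × 0.005 = 0.6 placebo (0 to 2).
- UTI: 120 × 0.264 = 31.7 active (22 to 41); 120 × 0.101 = 12.1 placebo (6 to 19).

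This assumes that the pooled rates apply to TC1 and that retention cases equal CIC users. If so, Table 3.134 has small cells, and one moved subject is 1/8.52 = 12% of active-arm CIC users. It does not say that anyone moves.

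**The case against.** The best defence is that the exclusion was written for by-visit displays. The section 8 sentence stands just before a table of display visits, whereas maximum PVR in TC1 is a cycle-level quantity in a more specific section. SAP 11.4.1.2 assigns non-AE safety data to a cycle by measurement date, and SAP 11.13 keeps some unscheduled records in the interim data. The SAP does not define an unscheduled visit, and the 1-week additional visit is directed by the protocol. A programmer could reasonably use every TC1 value.

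Part of this stands: the SAP admits two readings, and the loss of peaks is not certain. But a date rule for cycles and a data-cut rule do not lift an exclusion stated twice without exception, and 5.2 and 8.3 show that the SAP names its exceptions. Treating the additional visit as unscheduled is an inference. It is supported by the protocol's contrast between additional and regularly scheduled visits and by the visit list. Measurements on clinical need at unscheduled visits are caught either way.

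Two further points stand. The 2-week fallback means the Table 3.129 rule can be executed, so the issue there is which value it returns. And the PVR listing shows visit, date, value and a CIC-initiation flag, so a reader could reconcile individual subjects.

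A reader might infer that CIC and UTI would appear to arise at lower PVR than they did. The documents do not support that. The direction is fixed for one subject's category but not for row percentages (step 4), and the mock shells that might fix the denominator are in a separate document.

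**Conclusion.** The point holds as a minor one. Under the literal rule, a subject whose TC1 peak was measured off schedule and crossed a category boundary is classified too low in Table 3.134 or 3.139. Table 3.129 may report an earlier PVR than the one that triggered CIC. This rests on reading additional visits as unscheduled and on the exclusion reaching cycle-level maxima; the SAP text favours both without settling either. The number affected is unknown and may be zero.

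A reader might also infer that CIC use or retention is undercounted. It is not: CIC totals and retention events come from their own records, and subjects only move between rows of descriptive tables. No primary or other inferential result, adverse event rate or time to onset depends on this.

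**What to change.** State in SAP 8.5.1 to 8.5.3 that maximum PVR in TC1 and PVR at CIC start use all post-treatment TC1 measurements, scheduled and unscheduled, and that this overrides the general exclusion in 8 and 11.5.2, as 8.3 does for worst-case urinalysis. Keep the by-visit PVR tables on scheduled visits.

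The cost is one sentence and a few lines of programming. Unscheduled values already go to the listings, and SAP 11.13 shows that unscheduled records carry their own visit number (for example 1020.1), so they can be selected directly. No new data are needed.
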